### **5.4 Interim analysis**

No formal interim analysis is planned, however interim safety and efficacy results will be shared with a DSMB following a specific DSMB SAP and DSMB charter.

## 5.5 Baseline characteristics

### 5.5.1 Inclusion/exclusion criteria

An individual patient listing of deviations from the inclusion and exclusion criteria will be presented.

### 5.5.2 Demographics

Descriptive tabulations of the screening data for demographics will be made. Demographic data (including weight and height measurements) per treatment group and overall will be presented. Appropriate descriptive statistics for age, height, weight, BMI, race, ethnicity and gender will be given. Descriptive statistics will be n, arithmetic mean, SD, median, minimum and maximum for quantitative data. For qualitative data, frequency counts and percentages will be determined. The summary will be created for each efficacy analysis population separately. Additionally, demographic data will be listed.

### 5.5.3 Baseline characteristics

The patient baseline characteristic “substance use” and the stratification groups (the slope ALSFS-R score from the time of first symptoms until screening, concomitant use of riluzole) will be summarized per treatment group and overall using the safety population. Baseline characteristics will also be listed.

### 5.5.4 Disposition

To present disposition, a summary of all included, randomised, treated and completed patients will be created. Number/percentage screened will be included as well, if available in the database. Additionally, in the same summary, the number/percentage of patients in the ITT, mITT, PP, PK and SAF will be presented and the frequency/percentage per reason for non-completion will be added. The patient disposition will be presented per treatment group and overall.

Additionally, a listing displaying all disposition information (including reasons for withdrawal and reasons for exclusion from the PP population) on a per patient level will be created. This listing will include exposure time for each patient, calculated from date of first dose until end of treatment, and follow-up time for each patient, calculated from date of first dose until end of study.

### 5.5.5 Medical history

Medical history will be tabulated per System Organ Class (SOC) and Preferred term (PT) according to the Medical Dictionary for Regulatory Activities (MedDRA) terminology list and presented as number/percentage of patients in each SOC and PT for the SAF. SOC and PT will be presented in descending order of frequency of occurrence based on SOC and PT. These data will also be listed on a per patient level.

---

 A patient is considered to complete the study if he/she completed the 72 week treatment period OR if she/he completed at least 48 week of treatment at study completion (i.e. after the last patients have completed the study up to at least 48 week). Note that this is a different selection of patients than for the ‘Completer Analysis’ as defined as one of the sensitivity analyses.

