#### 6.5. Early Discontinuation/Withdrawal of Participants

Subjects may withdraw consent at any time for any reason or be dropped from the trial at the discretion of the investigator should any untoward effect occur. In addition, a subject may be withdrawn by the investigator or the Sponsor if enrolment into the trial is inappropriate, the trial plan is violated, or for administrative and/or safety reasons.

In this trial, a subject may discontinue from treatment but continue to participate in the regularly scheduled activities, as long as the subject does not withdraw consent. Once a subject has discontinued treatment, he/she may be allowed to start treatment again after consultation with the investigator, if discontinuation of treatment is  $\leq$  2 weeks.

A subject must be discontinued from the trial for any of the following reasons:

- The subject withdraws consent.
- The subject has a medical condition or personal circumstances which, in the opinion of the investigator and/or Sponsor, places the subject at unnecessary risk if participation in the trial is continued.
- The subject reaches the criteria for respiratory insufficiency (tracheostomy or the use of non-invasive ventilation for >20 hours per day for >10 consecutive days),

A subject must be discontinued from study treatment (but should continue to be monitored in the study) for any of the following reasons:

1-The subject becomes pregnant during the study.

2-The subject's investigator considers it is in the best interest of the subject to discontinue including worsening or disease progression if the investigator considers that it is in the patient's best interest the initiation of any standard of care treatment prohibited in the study

3-Serious adverse event considered related to the IMP

4-Severe Neurotoxicity considered related to the IMP

5-Any other severe adverse event considered related to the IMP at the discretion of the investigator.

6-Acute renal failure (creatinine clearance of less than 30 mL/min as calculated by the Cockcroft Gault equation)

7-Severe liver disorder defined as:

- ALT/AST  $\geq$  3xULN and bilirubin  $\geq$  2xULN ( $>35\%$  direct bilirubin)
- ALT/AST  $\geq$  8xULN
- ALT/AST  $\geq$  3xULN and with symptoms believed to be related to liver injury or hypersensitivity.
- ALT/AST  $\geq$  3x baseline ALT/AST and with symptoms believed to be related to liver injury or hypersensitivity.

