### **11.3.3. Subject Disposition**

Subject disposition (analysis population allocation, entered, discontinued, along with primary reason for discontinuation) will be summarized using frequency and percent for

---

both treatment and follow-up phase. A summary of subjects screened and enrolled will be provided.

A subject is considered to complete the study if he/she completed the 72 week period OR if she/he completed at least 48 week at study completion (i.e. after the last subjects have completed the study up to at least 48 week). Withdrawal from treatment or protocol deviations will not necessarily preclude from recording the respective follow-up information. Efforts will be made to follow all subjects up to 72 or 48 weeks after start of treatment (or to study end if that occurs earlier) and collect data as planned.

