### 11.4. Study Estimand and Handling of Missing Data

To be noted that in this study all efforts will be made to ensure collection of data up to week 48 for all randomized subjects and at least for 100 subjects up to week 72 regardless of treatment withdrawal or protocol deviations.

As per the ICH E9(R1) (*draft addendum on estimands and sensitivity analysis in clinical trials*), the plan for the assessment of the Primary endpoint (PEP) is described here after using the 4 attributes of the estimand:

1. Population: ALS patients fulfilling the selection criteria, as described in section 5 of this protocol
2. Primary endpoint (PEP): Change from baseline in Amyotrophic Lateral Sclerosis Functional Rating Scale – Revised (ALSFRS-R) score after 48 weeks (see sections 3.2.1 and 11.3.4.1)
3. Intercurrent events (IE): The assumptions and expectations on the relevant intercurrent for this study have been based on the publication of a similar trial (Cudkowicz et al., 2013)
4. Accordingly, the following situations have been identified:
  - a. No treatment initiation with the IMP: exclusion from the main analysis with the mFAS population.
  - b. Treatment discontinuation because of adverse events: expected rates  $\approx 3$  (control arm) - 7% (experimental arm).
  - c. Treatment discontinuation because of lack of efficacy: expected rates  $\approx 5$  (control arm) 10% (experimental arm).
  - d. Other treatment related reasons (i.e. due to efficacy or safety issues). To this category will apply other treatment related reasons that those specified in "b" and "c", even that, *a priori*, no potential scenarios are foreseen at the moment of the planning.
  - e. Rescue medication. No clear prevalence rates can be ascertained, but differential higher rates are expected in placebo. This situation is likely to be closely related to IE #c.
  - f. Non treatment-related reasons, others than specified in this list of IE: very low expected rates (i.e.  $\le 1\%$ ). This will also situations like patients moving (not because bad prognosis) to another location or death for completely treatment-unrelated reasons.
  - g. Related death (or death with unknown reasons): it is expected that the rate of death at 52 weeks will be lower than the observed in that trial ( $< 17\%$ ). A non-substantial but lower rate is expected in the experimental arm.

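### SAP 5.5.4, footnote 3, defines study completion by weeks of treatment where the protocol uses time in the study, so table 14.1.3 can understate study retention

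*SAP*

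**What the plan says.** Protocol 11.3.3 treats a subject as completing the study if "he/she completed the 72 week period OR if she/he completed at least 48 week at study completion". It does not mention being on drug. The same section states that "Withdrawal from treatment or protocol deviations will not necessarily preclude from recording the respective follow-up information", and it asks for disposition to be summarised for "both treatment and follow-up phase".

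The SAP attaches footnote 3 to the word for completed patients in 5.5.4 (the note is printed at the foot of that page, below 5.5.5). It follows the protocol sentence closely but adds treatment to both limbs: "A patient is considered to complete the study if he/she completed the 72 week treatment period", or if the patient "completed at least 48 week of treatment at study completion". The footnote still calls this completing the study.

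SAP 5.5.4 then describes one summary of completed patients with reasons for non-completion, by arm and overall. SAP 10.3 marks this output, table 14.1.3, as topline. SAP section 6 lists changes from the protocol, including corrected typing errors, but not this one.

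**The concern.** The plan deliberately creates patients who are off drug and still in the study. Protocol 6.5 says that "a subject may discontinue from treatment but continue to participate in the regularly scheduled activities". Protocol 11.4 plans data collection to week 48 "regardless of treatment withdrawal or protocol deviations". Under SAP 5.1, patients taken off drug after two missed visits can still give ALSFRS-R by telephone, and those data are accepted as equal in quality. Such a patient can supply an observed week-48 value of the primary endpoint and still be reported as not having completed the study.

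The primary strategy for stopping treatment is Treatment Policy. A reader judges that estimand partly by how many patients in each arm were followed to week 48. A count of treatment persistence labelled as study completion answers a different question. It understates retention in any arm where someone is followed after stopping drug. If stopping differs by arm, it can also make retention look more unequal than it is.

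**Working it through.** **1. The plan's own figure.** Arm sizes of 200 and 100 are the denominators below, so I checked them first. Inputs from protocol 11.2: difference 3.0, SD 7.5, two-sided 5%, 90% power, ratio 2:1.

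- Placebo n = (1 + 1/2) × 7.5² × (1.960 + 1.282)² / 3.0² ≈ 98.5, rounded up to 99. With 198 on FAB122 the total is 297, against the stated 300.
- At 200 and 100, SE = 7.5 × √(1/200 + 1/100) = 0.919. Then 3.0/0.919 − 1.960 = 1.306, giving power of 0.904. The stated figures reproduce.

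**2. Expected stops of treatment (protocol 11.4).** Adverse events: 7% FAB122, 3% placebo. Lack of efficacy: 10% and 5%. Summed as mutually exclusive:

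- FAB122: 7% + 10% = 17%, or 34 of 200.
- Placebo: 3% + 5% = 8%, or 8 of 100.

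**3. Classification under each definition.** Let f be the share of these patients followed to week 48, taken as equal in both arms. The documents give no value, so f runs from 0 to 100%.

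- SAP wording: all are non-completers, 17% against 8%, a gap of 9.0 points whatever f is.
- Protocol wording: non-completion is 17% × (1 − f) against 8% × (1 − f).
- Gap due only to the definition: (17% − 8%) × f.

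| f | Mislabelled, FAB122 | Mislabelled, placebo | Non-completion, protocol wording (FAB122 vs placebo) | Gap, protocol wording | Gap due to definition |
|---|---|---|---|---|---|
| 0% | 0 | 0 | 17% vs 8% | 9.0 | 0 |
| 25% | 8.5 | 2 | 12.75% vs 6% | 6.75 | 2.25 |
| 50% | 17 | 4 | 8.5% vs 4% | 4.5 | 4.5 |
| 75% | 25.5 | 6 | 4.25% vs 2% | 2.25 | 6.75 |
| 100% | 34 | 8 | 0% vs 0% | 0 | 9.0 |

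At f = 50%, 17 + 4 = 21 patients are mislabelled; at 100%, 34 + 8 = 42. Deaths and withdrawals from the trial before week 48 are left out because they are non-completers under either wording.

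**4. What else shows retention.** The 5.5.4 listing gives exposure time and follow-up time separately, but per patient. Protocol 11.3.6 asks for reasons for stopping study drug to be tabulated. SAP 10.3 names no such table apart from 14.3.1.8, which covers adverse events only. The ALSFRS-R descriptives (14.2.1.1 onward, topline) show non-missing counts by visit and arm under SAP 5.1, 5.2 and 5.6.

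**5. What uses the footnote.** The primary MMRM and its imputation, CAFS and survival time do not refer to it. The Completer analysis in SAP 5.2 has its own rule, and footnote 3 itself says that analysis selects different patients.

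**The case against.** The strongest reply is that the wording differs but little follows from it.

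- *Retention is visible elsewhere.* This stands. Week-48 ALSFRS-R counts by arm are in the same topline package, so a careful reader can recover follow-up. They do not give reasons, and they do not correct a row labelled as study completion.
- *The footnote may be loose drafting.* The visit schedule heads all post-baseline visits as the treatment period, so the first limb could mean the visit period. The second limb, which counts weeks of treatment, is hard to read that way. If only drafting is at fault, the same edit cures it.
- *The table may separate the two.* SAP 10.1 puts table templates in a separate document, which is not available here. Section 5.5.4 describes a single completed count, so separate rows cannot be assumed.
- *An imbalance is not shown.* This stands. A reader might infer that the SAP will produce a false drop-out imbalance, with completion of 83% against 92% where the truth is 100% against 100%. The documents do not support that. It requires every patient who stops drug to be followed to week 48, whereas protocol section 4 promises follow-up only as far as possible and the primary analysis provides for patients with no data after stopping. The rates are planning expectations taken from another trial. Protocol 11.4 also expects more rescue medication on placebo, and protocol 6.5 lists starting riluzole as a reason for stopping study drug, so placebo stops could narrow the gap. A real excess of stops on FAB122 would itself be a finding worth reporting; only the label would be wrong.

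**Conclusion.** The point holds as a reporting error. Footnote 3 changes the protocol's criterion from time in the study to weeks on treatment, without declaring it, and conflicts with the protocol's request to report both phases. Read literally, it understates study retention in topline table 14.1.3 whenever a patient is followed to week 48 off drug.

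The between-arm gap created by the definition alone is somewhere from 0 to 9.0 points, and 4.5 if half are followed. This rests on three assumptions: the planning rates of 17% and 8%, the two reasons being mutually exclusive, and the same follow-up share in each arm. If stopping rates and follow-up shares are equal between arms, the definition adds no gap, although retention is still understated in both. The protocol's expectation of very little missing data points towards a high follow-up share but does not quantify it.

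It would be wrong to infer that any efficacy result is affected. The primary, CAFS, survival and Completer analyses and the sample size do not depend on this footnote.

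**What to change.** In footnote 3, restore the protocol 11.3.3 wording by deleting *treatment* from the 72-week limb and *of treatment* from the 48-week limb. In table 14.1.3, show two separate blocks by arm, each with its reasons: completed study treatment, and completed study follow-up (week 48, or week 72 for the first 100 patients). If a treatment-based count was intended, label it treatment completion and declare it in SAP section 6.

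The cost is one footnote and one block of table rows. No new data are needed, because the 5.5.4 listing already requires both the end-of-treatment and the end-of-study date for each patient.

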### **5.5.6 ALS history**

Collected information on ALS history will be summarized as appropriate. ALS duration will be determined based on the baseline data and the date of onset. In case of (partially) missing onset date, the imputation rules per section 5.2 will be followed.

### **5.5.7 Other screening data**

Not applicable.

## **5.6 Statistical analysis primary and secondary endpoints**

The primary analysis population is the mITT for the primary and all secondary endpoints. Analyses of the primary endpoint based on the ITT and PP will also be undertaken to provide supplementary information on efficacy. Statistical analysis on secondary endpoints will be considered explorative in nature and will only be done for the mITT.

For each of the primary and secondary endpoints descriptive statistics will be presented for original values and change from baseline values on a per-visit basis, for each treatment arm and overall. All individual primary and secondary endpoint data will be listed as well.

No multiple corrections will be applied: a hierarchical approach is used as per section 4.1 and all other endpoints are considered strictly explorative.

### **5.6.1 Primary analysis**

The primary endpoint is defined as the change from baseline in total ALSFRS-R score after 48 weeks (primary timepoint).

For the primary analyses, a placebo (reference) multiple imputation (pMI) will be applied to impute missing data for any patients (i.e. from both treatment arms) who discontinue treatment early, irrespective the reason for drop-out (only when due to intercurrent events with unknown cause), and for which no data was collected after treatment discontinuation. The pMI method assumes the statistical behavior of placebo- and drug-treated patients after dropout is the statistical behavior of placebo-treated patients. A total of 20 imputed data sets will be created.

Before applying the statistical model to the primary endpoint, intercurrent events will be handled following the rules specified in Section 5.2.

The primary endpoint will be analyzed using a mixed model for repeated measures (MMRM), considering ALSFRS-R is assessed at multiple timepoints. The average treatment effect (lsmeans) and the treatment difference (estimand) of the change from baseline ALSFRS-R total score at 48 weeks will be extracted from the results from this model and presented together with the 95% confidence interval and p-value. Other timepoints will also be presented.

The model will include factors for treatment, time, treatment-by-time interaction, the stratification factor concomitant use of riluzole (yes/no), baseline ALSFRS-R score and the stratification factor slope of disease progression as fixed effects. An unstructured (UN) covariance matrix will be used in the model. If the model does not converge, the structure will be adapted to respectively AR(1), Toeplitz or Compound Symmetry (CS). The results of the 20 imputed data sets will be combined to obtain the final estimate of the treatment difference with 95% confidence interval and p-value.

An example SAS code which can be used as basis is as follows:

```
proc mixed data=<data>;
  class trt time riluse;
  model cfb=trt time trt*time riluse base disslope / ddfm=kr;
  repeated time/ subject=patient type=un;
  lsmeans trt*time/cl;
run;
```

Sensitivity analyses using the mITT population will be performed for the primary endpoint as described in Section 5.2. The same model will be used to each of the imputed datasets separately after applying the imputation techniques. The estimated parameters of the imputed datasets will be pooled using Rubin's combining rules to obtain a final result of the treatment difference with a 95% confidence interval and p-value.

Descriptive statistics will be presented for ALSFRS-R total score, including change from baseline.

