##### **11.3.4.2. Primary Efficacy Endpoint**

The primary endpoint is defined as the change from baseline in ALSFRS-R score after 48 weeks (primary time point).

For the primary analyses placebo (reference) multiple imputation will be applied to impute missing data for any subjects (i.e. from both treatment arms) who discontinue treatment early, irrespective the reason for drop-out, and for which no data was collected after treatment discontinuation. A total of 20 imputed data sets will be created.

Linear mixed modelling for repeated measures will be applied on each of the imputed data set to estimate the average (lsmeans) treatment effects and the treatment difference (estimand) of the change from baseline of ALSFRS-S score at week 48.

The model will include factors for treatment, time, treatment-by-time interaction, and concomitant use of riluzole (yes/no) as fixed effects and baseline ALSFRS-R score and slope of disease progression (based on change in ALSFRS-R score) as (random) covariates.

The results of the 20 imputed data sets will be combined to obtain the final estimate of the treatment difference with 95% confidence interval and p-value.

The primary analysis will be performed on the modified intent-to-treat population (mITTs), i.e. all randomized patients who had at least one treatment intake

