The primary strategy for handling the IE will consist of the "Treatment Policy" strategy applied for all these intercurrent events, i.e., the efficacy observed assessment will be used regardless of the intercurrent event. Therefore, overall the amount of missing data generated will be a very small. For these cases a placebo (copy from reference) multiple imputation will applied. A total of 20 imputed data sets will be created.

However, it is noted that the "Treatment Policy" strategy will not be applicable for terminal intercurrent events such as death (IE #g) or when there are real lost to follow-up cases after doing all efforts to retrieve the data (some cases in IE #f). For cases with missing data in IE #f, the same general approach as described above will be implemented. For related death (IE #g) it is proposed to use a "Composite strategy" and thus a conservative scenario using a 95th worst percentile combined with multiple to avoid variance artefactual shrinking.

---

- h. Population-level summary: the change from baseline in ALSFRS-R score after 48 weeks (primary time point), using a linear mixed modelling for repeated measures. The model will include factors for treatment, time, treatment-by-time interaction, and concomitant use of riluzole (yes/no) as fixed effects and baseline ALSFRS-R score and slope of disease progression (based on change in ALSFRS-R score) as (random) covariates (see section 11.3.4.1)).

To evaluate the impact of missing data and of the handling methods, a number of sensitivity analyses will be performed for the primary endpoint:

- **As treatment multiple imputation:** For any subject with missing values, the estimates for the missing assessments will be based on the actual treatment group of that subject. One hundred imputations will be performed.

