## 5.2 Missing or excluded data or intercurrent events

### *Efficacy data – intercurrent events*

The intercurrent events during the study can be broadly classified as terminal and non-terminal intercurrent events. Death or “real” loss to follow-up are considered terminal intercurrent events, wherein there is absolutely no data available for these patients after the occurrence of the event. The other intercurrent events are non-terminal, where there is a possibility of collecting data from these patients after the occurrence of the intercurrent event (ICE).

Note that per design of the study, only 100 patients will be followed until week 72. The non-available data for the ~200 patients between week 48 and 72 will not be considered as ICE.

Regarding intercurrent events, following ICH E9 (R1), two types of strategies will be applied for the primary statistical analysis performed for the primary endpoint and utilizing the primary analysis population (mITT).

The “Treatment Policy” strategy will be applied to the following intercurrent events:

- Treatment discontinuation due to adverse events.
- Treatment discontinuation due to lack of efficacy.
- Other unforeseen treatment related reasons (i.e. due to efficacy or safety issues).
- Rescue medication.
- Non-treatment-related reasons, other than those already specified earlier. This includes situations like patients moving to another location for treatment unrelated reasons. Note that the “Treatment Policy” strategy might not be applicable if there are real lost-to-follow-up cases after doing all efforts to retrieve the data.

For deaths, the Treatment Policy cannot be applied, and missing data imputation will be used for the statistical analyses.

The “Treatment Policy” strategy implies that the efficacy observed assessment (including those collected after the occurrence of the intercurrent event) will be used regardless of the occurrence of an intercurrent event.

The “Composite” strategy will be applied to the following intercurrent events.

- Related death (or death with unknown reasons). It is expected that the rate of death at 52 weeks will be lower than that observed in the trial (<17%). A non-substantial but lower rate is expected in the experimental arm.
- “Real” lost to follow-up. These are cases where there is lost to follow-up after reasonable attempts to contact the patient have been made and all efforts to retrieve the data have failed.

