The “Composite” strategy for handling these events will be applying a conservative scenario using the 95% worst percentile combined with multiple imputation (the intercurrent event is explicitly taken into account and made part of the outcome by this imputation, conditioned on timepoint). This method uses the imputation of a conservative value representing the 95th worst percentile.

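### SAP 5.6.1 both includes and excludes adverse-event and lack-of-efficacy drop-outs from placebo imputation, and SAP section 6 omits two related departures from the protocol

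*SAP*

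**What the plan says.** **Protocol.** Section 11.3.4.2 applies placebo multiple imputation in both arms to early treatment discontinuations, "irrespective the reason for drop-out, and for which no data was collected after treatment discontinuation". Section 11.4 uses a treatment-policy strategy for intercurrent events and, for whatever remains missing, states "For these cases a placebo (copy from reference) multiple imputation will applied". It recognises that some patients in IE #f (reasons unrelated to treatment, which there include wholly unrelated deaths) will be truly lost, and adds "For cases with missing data in IE #f, the same general approach as described above will be implemented". The worst-percentile composite is kept for related or unexplained death (IE #g).

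**SAP 5.6.1.** The protocol sentence reappears with an insertion: "irrespective the reason for drop-out (only when due to intercurrent events with unknown cause), and for which no data was collected after treatment discontinuation". The section then says "Before applying the statistical model to the primary endpoint, intercurrent events will be handled following the rules specified in Section 5.2".

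**SAP 5.2.** Discontinuation for adverse events or lack of efficacy falls under Treatment Policy. That "strategy implies that the efficacy observed assessment (including those collected after the occurrence of the intercurrent event) will be used". Real loss to follow-up is listed under Composite: "These are cases where there is lost to follow-up after reasonable attempts to contact the patient have been made". Composite handling means "applying a conservative scenario using the 95% worst percentile combined with multiple imputation". Footnote 2 extends it to all deaths, including unrelated ones.

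**SAP section 6.** The list of changes from the protocol covers the hybrid approach, CAFS, mis-randomised patients, CTCAE grades and typing corrections. It does not mention the parenthesis, loss to follow-up or unrelated deaths.

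**The concern.** A rule cannot apply whatever the reason and also only for certain reasons. Adverse event and lack of efficacy are known causes, so the first half of the sentence brings these patients into placebo imputation and the parenthesis takes them out. Protocol 11.4 expects both reasons more often on FAB122 (7% and 10%) than on placebo (3% and 5%), so the choice does not affect the arms equally.

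The primary endpoint is step I of the fixed sequence, and later steps are confirmatory only if it succeeds. SAP 5.6.2 reuses the 5.6.1 imputation for survivors without a week-48 score before CAFS (step II) is ranked. SAP 5.2 carries the same rules into the PP and ITT analyses. Two programmers could therefore follow the text in good faith and obtain different confirmatory p-values, and a choice made after unblinding would not be pre-specified.

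**Working it through.** **1. Does the text settle the rule?**

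| Patient with no later ALSFRS-R | Protocol | SAP |
|---|---|---|
| Stopped for adverse event or lack of efficacy | Placebo imputation (11.3.4.2, 11.4) | Included and excluded in one sentence (5.6.1); Treatment Policy in 5.2, which covers observed scores only |
| Real loss to follow-up | Placebo imputation (11.4, IE #f) | Worst-percentile composite (5.2) |
| Treatment-unrelated death | Placebo imputation (11.4, IE #f) | Worst-percentile composite (5.2, footnote 2) |

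The cross-reference from 5.6.1 to 5.2 does not help with the first row, because 5.2 gives no primary-analysis rule for scores that were never collected. If the parenthesis is obeyed, two fallbacks remain: implicit missing-at-random handling in the MMRM, or the composite if the patient is also classed as really lost.

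**2. Reproduce the plan's figure.** Inputs from Protocol 11.2 and SAP 2.4: difference 3.0, SD 7.5, 200 and 100 patients, two-sided 5%.
- SE = 7.5 × √(1/200 + 1/100) = 0.919.
- Power = Φ(3.0/0.919 − 1.96) = 90.4%, matching the stated 90%.

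**3. Missing at random against placebo imputation.** Expected FAB122 discontinuation for the two reasons is 7% + 10% = 17% (34 of 200). The documents do not give the share with no later score, so 25% and 50% are assumed. As an upper bound, placebo imputation is taken to remove the whole 3.0-point benefit for these patients. Placebo patients are imputed from their own arm either way, so their rate does not enter the shift.
- Shift = 0.17 × share × 3.0.
- 25%: 0.17 × 0.25 × 3.0 = 0.13 points; power Φ((3.0 − 0.1275)/0.919 − 1.96) = about 88%.
- 50%: 0.17 × 0.50 × 3.0 = 0.26 points; power Φ((3.0 − 0.255)/0.919 − 1.96) = about 85%.

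If the imputation model conditions on earlier scores, some benefit is retained and the shift is smaller.

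**4. The other fallback.** Assume mean changes of −9 and −12 (Protocol 11.2: placebo loses 12 points in 12 months) and a pooled percentile value of −10 − 1.645 × 7.5 = −22.3. The SAP does not define the reference distribution. If the same shares (of 17% on FAB122 and 8% on placebo) went to the composite, the expected difference would be 2.64 at 25% and 2.28 at 50%. This would require that many patients to be untraceable, whereas Protocol 11.4 places real losses among only some cases of a category expected at 1% or less.

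**5. Loss to follow-up alone.** At 1% in each arm:
- Placebo imputation: 3.0 − 0.01 × 3.0 = 2.97.
- Composite: (0.99 × −9 + 0.01 × −22.3) − (0.99 × −12 + 0.01 × −22.3) = 0.99 × 3.0 = 2.97.

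The change has practically no effect when losses are balanced.

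**The case against.** The strongest defence is that SAP section 1 says the SAP agrees with protocol version 4.0 and takes the protocol as a primary source. The protocol is unambiguous, and the SAP repeats its wording on reason for drop-out. The SAP also labels an explicitly missing-at-random imputation as a sensitivity analysis, which suggests that the primary analysis is meant to differ. This makes placebo imputation the likelier intention. A general statement of agreement does not cancel a specific restriction added to the primary-analysis rule, however, and SAP section 6 shows that the SAP departs from the protocol elsewhere.

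Second, few patients should be affected. ALSFRS-R can be collected by telephone after study drug stops, follow-up continues after treatment withdrawal, and Protocol 11.4 expects very little missing data. The hybrid analysis (placebo-based for these two reasons) and the as-treatment imputation (own arm) probe both main readings. All of this stands and limits the size of the problem. It does not say which p-value is confirmatory.

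Third, the composite is stated openly in SAP 5.2, footnote 2 explains the extension to all deaths, and the version 4.0 history entry mentions changes to the primary analysis. That entry is too general to identify either change. What remains for these items is an incomplete change list, together with an undefined percentile reference and step order.

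**Conclusion.** The point holds. SAP 5.6.1 contradicts itself on a class of patients for whom the protocol is clear, and two changes of imputation rule are missing from SAP section 6. The effect is likely small: at most about 0.13–0.26 points and 3 to 6 percentage points of power for missing-at-random against placebo imputation, and close to nil for balanced loss to follow-up at the expected rate. These figures rest on the protocol's expected discontinuation rates, the design effect of 3.0, SD 7.5, and an assumed 25–50% without later data. The documents suggest that the true share is low.

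Three stronger inferences are not supported:
- That the SAP has switched these patients to missing-at-random. It names no replacement, and its description of terminal events as leaving no data at all could send untraceable drop-outs to the composite.
- That moving losses to the composite works against FAB122. No passage gives loss rates by arm.
- That the effect can be stated precisely. It depends on a share and a variance structure that the documents do not supply.

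**What to change.** Before unblinding:

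1. In SAP 5.6.1, delete the parenthesis. State that placebo multiple imputation applies to every missing week-48 ALSFRS-R after treatment discontinuation, whatever the reason, except events assigned to the composite in 5.2. This also covers patients with some later scores but none at week 48, in line with the general missing-data rule in Protocol 11.4.
2. Use one rule for real loss to follow-up in 5.2 and 5.6.1: either placebo imputation as in Protocol 11.4, or the composite listed in section 6 as a departure. List the treatment-unrelated-death change there too.
3. State the order of the composite and placebo-imputation steps, and the reference distribution for the percentile (placebo, FAB122 or pooled).

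The cost is SAP wording only. No new data, visits or patients are needed.
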